12.1.2. Primary Effectiveness Endpoint

The primary effectiveness endpoint of this study is:

- LV pacing threshold measurements performed at 0.5 ms pulse width at 3 months post-implant

The pacing configuration that the physician selects for permanent programming will be compared to prospectively determined limits.

12.1.2.1. Hypotheses

The null and alternative hypotheses are as follows:

H_0 : The mean LV pacing threshold at 3 months \geq 2.5V

H_A : The mean LV pacing threshold at 3 months $<$ 2.5V

The null hypothesis (H_0) will be rejected if the upper one-sided 95% confidence bound for the mean LV pacing threshold is less than the performance goal of 2.5V.

12.1.2.2. Statistical Methods

When the final study subject reaches the 3 Month required follow-up visit, the primary effectiveness analysis will be performed based on one-sample t-test methodology for the

comparison of the mean LV pacing threshold, including the upper one-sided 95% confidence bound. Implanted subjects with available LV pacing threshold at the 3-month endpoint evaluation (91 days \pm 21 days post-implant) will be included in the analysis. The sample size was adjusted to account for up to 20% attrition to ensure there would be a sufficient number of evaluable subjects at 3-months.

The primary effectiveness endpoint will evaluate the mean LV pacing threshold at 3-months post-implant, and comparison will be performed using one-sample t-test methodology. The null hypothesis will be rejected and the endpoint considered met if the upper one-sided 95% confidence bound for the mean LV pacing threshold at 3-months is less than 2.5V.

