Statistical Test Method	
Sample Size Methodology:
 
 • Sample size for the primary safety endpoint was calculated using exact binomial methods for comparison of a single proportion to a performance goal. • Sample size for the primary effectiveness endpoint was calculated using one-sample t-test methodology for comparison of a single mean to a performance goal. 
Analysis Methods:
 
 • The DRCFR from implant will be calculated as the proportion of actively enrolled subjects without a device-related complication through 3 months after implant. The null hypothesis will be rejected and the endpoint considered met if the lower one-sided 95% confidence bound for the proportion of subjects with no device-related complication is greater than 87.5%. • Regarding mean LV pacing threshold at 3 months post-implant, the null hypothesis will be rejected and this endpoint considered met if the upper one-sided 95% confidence bound for the mean LV pacing threshold at 3-months is less than 2.5V. 
Further details on analytical methods can be found in Section 12.0 of the CIP.

Sample Size Parameters	
DRCFR through 3 months post-implant: 62 subjects. Sample size was calculated assuming a 97.5% DRCFR, a performance goal of 87.5%, one-sided alpha level of 0.05, 80% power, and 20% attrition.
 
Mean LV pacing threshold at 3 months post-implant: 45 subjects. Sample size was calculated assuming a mean (\pm standard deviation [SD]) LV pacing threshold of $1.9 \pm 1.2V$, a performance goal of 2.5V, one-sided alpha level of 0.05, 90% power, and 20% attrition.
 
Based on the above sample size calculations, the minimum required sample size to statistically power the primary endpoints is 62 subjects.

3. Table of Contents

1. TITLE PAGE	1
2. CLINICAL INVESTIGATION PLAN SYNOPSIS	4
3. TABLE OF CONTENTS.....	10
3.1. Table of Figures.....	13
3.2. Table of Tables	14
4. INTRODUCTION	15
5. DEVICE DESCRIPTION.....	18
5.1. Ingenio 2 Cardiac Resynchronization Therapy Pacemakers.....	18
5.1.1. PaceSafe.....	21
5.1.2. Post-Operative System Test.....	21
5.1.3. Atrial Arrhythmia Reports	22
5.1.4. ECG/EGM Snapshots	22
5.1.5. Leads.....	22
5.1.6. ZIP Telemetry	22
5.1.7. Programming System.....	22
5.2. Ingenio 2 CRT-P Indications for Use	23
5.3. Ingenio 2 CRT-P Contraindications.....	24
6. STUDY OBJECTIVE	24
7. ENDPOINTS	24
7.1. Primary Safety Endpoint.....	24
7.2. Primary Effectiveness Endpoint	24

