11.5. Implant Procedure (Day 0; required); Re-implant/Revision Procedures (as needed)

Subjects that meet all of the entry criteria and consent to the procedure are eligible. All subjects will be implanted, per center SOC procedure, with one of 3 Rally CRT-P models; selection of subject appropriate device will be at the discretion of the Investigator based on appropriate medical considerations. All future follow-ups will be based on this date.

Subjects that need re-implant or revision procedures, as determined by the Investigator, will undergo the same procedures as described for Day 0. The reason for re-implant/revision is to be documented in the eCRF.

While the Investigator should follow the center's SOC procedures and the IFU, it is important to ensure that the pulse generator has good contact with the surrounding tissue of the implantation pocket, and then suture it in place to minimize device migration (Figure 5-2).

In addition, two strategies are recommended for device configuration and programming:

- 1) Non-apical, non-septal-pacing vector, AV optimization, Echocardiographic optimization, QLV optimization any acceptable pacing threshold and no PNS
- 2) Non apical pacing vector, no further optimization, good pacing threshold and no PNS.

All standard lead/device components are to be assessed during and/or after implant.

The following data elements will be captured DURING the index procedure:

- Procedure time skin to skin, number of LV lead repositioning attempts
- Model and serial number of all implanted and active devices
- Final LV pacing configuration: impedance and threshold
- Final sensing configuration LV-R-wave
- Artifacts during sensing post-implant (ADE reporting)
- Confirmation /assessment of MICS, lead insertion, header
(all lead insertion difficulties or ball seal problems (including but not limited to: missing springs, dislodged springs, etc.) must be reported as an event. The subject impact should be documented in the event description.
- Bipolar sensing amplitude for right atrial (RA) and right ventricle (RV) electrodes should be measured and recorded
- Occurrence of any device-related event (unanticipated serious adverse device effect [USADE], ADE, DD) or SAEs unrelated to the device

The implant procedure will be noted in the eCRF as intended, attempted or successful.

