12.3. Sample Size

The minimum required sample size to evaluate the primary endpoints and account for up to 20% attrition is 62 (Table 12-1).

Table 12-1: Endpoint Sample Size Estimates

Endpoint	Measurement	Hypotheses ¹	Expected Performance	Power	Number of Subjects	
					needed for analysis	to be enrolled for ≤ 20% attrition
Primary Safety Endpoint	DRCFR from 0 to 3 months	$H_0: \text{DRCFR} \leq 87.5\%$ $H_A: \text{DRCFR} > 87.5\%$	97.5%	80%	49	62
Primary Effectiveness Endpoint	LV pacing threshold at 3 months	$H_0: \text{mean} \geq 2.5\text{V}$ $H_A: \text{mean} < 2.5\text{V}$	$1.9 \pm 1.2\text{V}$	90%	36	45

¹ Hypothesis test based on a one-sided alpha level of 0.05.

LV=left ventricular; DRCFR=device-related complication free rate

Sample sizes were calculated employing exact binomial methods (primary safety endpoint) and one-sample t-test methodology (primary effectiveness endpoint) in nQuery 6.0.

The following assumptions were used for the calculation of sample sizes:

- Primary Safety Endpoint
 - Expected DRCFR = 97.5% (determined from prior comparable BSC devices)
 - Performance goal = 87.5% (clinically accepted delta of 10%, subtracted from expected DRCFR)
 - Test significance level (α) = 0.05 (one-sided)
 - Power = 80%
- Primary Effectiveness Endpoint
 - Expected mean (\pm standard deviation [SD]) LV pacing threshold = $1.9 \pm 1.2\text{V}$ (based on prior BSC LV lead performance)
 - Performance goal = 2.5V (used in prior BSC led approval studies)
 - Test significance level (α) = 0.05 (one-sided)
 - Power = 90%

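### The primary effectiveness analysis has no rule for LV leads revised before 3 months, so a threshold that failed and was corrected does not reach the 2.5 V test

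*Combined protocol and SAP*

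**What the plan says.** The endpoint in Section 12.1.2 is "LV pacing threshold measurements performed at 0.5 ms pulse width at 3 months post-implant". The vector scored is left to the physician: "The pacing configuration that the physician selects for permanent programming will be compared to prospectively determined limits".

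Section 12.1.2.2 applies a one-sample t-test. The endpoint is met if the upper one-sided 95% confidence bound is below 2.5 V. The subjects analysed are "Implanted subjects with available LV pacing threshold at the 3-month endpoint evaluation", at 91 ± 21 days after implant. Sections 12.1.2 to 12.1.2.2 and 12.4.1 (Analysis Sets) do not say how to score a subject whose LV lead was revised before that visit. They give no failure score, do not use the pre-revision value, and plan no sensitivity analysis.

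The plan does expect revisions. Section 11.5 says: "Subjects that need re-implant or revision procedures, as determined by the Investigator, will undergo the same procedures as described for Day 0", and asks for the reason to be recorded. Table 11-1 provides for re-implant/revision, and Table 25-2 defines lead revision/reposition. Section 18.1 lists elevated thresholds, loss of capture and lead dislodgment as potential events.

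The sample size rests on an expected 1.9 ± 1.2 V and "a performance goal of 2.5V, one-sided alpha level of 0.05, 90% power, and 20% attrition". Table 12-1 gives 36 subjects for analysis and 45 enrolled for this endpoint, and 49 and 62 for safety.

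**The concern.** An elevated LV threshold or loss of capture is a reason to revise an LV lead, so the intervention can be set off by the very variable the endpoint measures. After revision, the value available at 3 months describes the corrected lead. If there is no value in the window, the subject leaves the analysis. In neither case does the poor threshold contribute to the mean, so the error runs in one direction, toward meeting the 2.5 V goal.

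This differs from ordinary missing data. Most revised subjects will have a 3-month value and will look complete, so a count of missing thresholds would not reveal them. A report of a mean below 2.5 V could not show how far the result depends on corrected leads.

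**Working it through.** **Inputs from the documents**
- Expected mean 1.9 V, SD 1.2 V, goal 2.5 V, one-sided alpha 0.05 (synopsis; Section 12.3).
- Evaluable n: 36 for this endpoint, and 49 if the study enrols 62 and loses 20% (Table 12-1).
- Range for a failing threshold: 3.5 V, the follow-up cut-off for an elevated threshold (Table 25-2), to 7.5 V, the highest value LVAT can measure (Section 5.1.1).

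**Assumed:** the number revised (k); a failing value V of 3.5, 5 or 7.5 V for every revised subject; post-revision values that behave like those of unrevised subjects.

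**Step 1. The plan's own figure.** A noncentral-t calculation with difference 2.5 − 1.9 = 0.6 V and SD 1.2 V gives n = 36 with power 90.3%. Then 36/0.8 = 45. The stated 36 and 45 reproduce, so the sample size is not in question.

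**Step 2. Bound as planned**, with revised subjects scored post-revision. Upper bound = mean + t(0.95, n−1) × SD/√n.
- n = 49: 1.9 + 1.677 × 1.2/7 = 2.188 V (met).
- n = 36: 1.9 + 1.690 × 1.2/6 = 2.238 V (met).

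**Step 3. Bound with k revised subjects scored at V.** Let m = n − k.
- Mean M = (1.9m + kV)/n.
- Sum of squares = 1.44(m − 1) + m(1.9 − M)² + k(V − M)².
- SD = √(sum of squares/(n − 1)).

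Example with n = 49, k = 5, V = 5:
- M = (83.6 + 25)/49 = 2.216 V.
- Sum of squares = 61.92 + 4.40 + 38.74 = 105.07, so SD = √(105.07/48) = 1.479 V.
- Bound = 2.216 + 1.677 × 1.479/7 = 2.571 V (not met).

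The same formula finds where the result turns:

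| n | V | Largest k still met (bound) | Smallest k not met (bound) |
|---|---|---|---|
| 49 | 3.5 V | 9 (2.493 V) | 10 (2.526 V) |
| 49 | 5 V | 4 (2.497 V) | 5 (2.571 V) |
| 49 | 7.5 V | 1 (2.357 V) | 2 (2.517 V) |
| 36 | 3.5 V | 5 (2.473 V) | 6 (2.518 V) |
| 36 | 5 V | 2 (2.458 V) | 3 (2.564 V) |
| 36 | 7.5 V | 1 (2.480 V) | 2 (2.703 V) |

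**Step 4. Chance of a false pass.** Suppose the mean including failing thresholds is exactly 2.5 V and a fraction f is revised. The mean of the scored values is then (2.5 − fV)/(1 − f); for f = 5% and V = 5 V it is 2.25/0.95 = 2.368 V. With SD 1.2 V and n = 49, the probability of meeting the endpoint, nominally 5%, is:

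| V | 2% revised | 5% revised | 10% revised |
|---|---|---|---|
| 3.5 V | 6.3% | 9.0% | 15.7% |
| 5 V | 8.8% | 18.7% | 48.1% |
| 7.5 V | 14.5% | 44.8% | 93.9% |

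Leaving revised subjects out instead gives nearly the same result (at 5 V: 8.8%, 18.3% and 44.7%).

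**The case against.** **The endpoint may be meant this way.** The threshold at 3 months in the permanently programmed configuration is a coherent measure of the system in use. The study device is a pulse generator that may be used with any commercially available LV lead (Section 5.1.5), so repositioning a lead is not clearly a failure of that device. The 2.5 V goal comes from earlier sponsor studies whose handling of revised leads is not described, so scoring failures in the primary test could break comparability with the goal. This stands. It is why the repair is a sensitivity analysis and the planned test is kept.

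**A reader might infer that revision restarts the visit clock and removes the subject.** Section 11.5 covers implant and revision under one heading and says "All future follow-ups will be based on this date", and Table 11-1 puts both in one column. The documents do not support a restart as a rule. That sentence closes the paragraph on the implant, and the later sentence on revision repeats the procedures, not the date. The synopsis schedule and Section 11.1 tie follow-up to the Day 0 implant and list re-implant/revision separately. Drop-out by this route would also need visits to be re-dated while the analysis window stayed on the first implant. What remains is a small ambiguity worth one clarifying sentence.

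**A reader might infer that the failure counts nowhere.** That is true only of the effectiveness mean. Section 19.1 gives surgical lead revision as an example of a complication, and Section 12.1.1 allows events listed in Section 18.1 to count against the DRCFR. The cover is partial: the complication must be assessed as related to the Ingenio 2 CRT-P device, so a revision attributed to the LV lead may not count.

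**The size is hypothetical.** This also stands. The documents give no revision rate, and at the planned mean one revision does not change the result anywhere in the range examined.

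**The last recorded value may miss the failure.** Table 11-1 does not require LV or manual thresholds at unscheduled visits. After a day-60 revision, the last required value may be the 1-month one, taken before the lead failed. Section 5.1.2 says LVAT does not cover X4 leads, and loss of capture may leave no number at all. The objection is sound, and the repair needs a failure-value version as well.

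**Conclusion.** The concern holds for the primary effectiveness mean. The plan foresees LV lead revision in its procedures but not in its analysis, and the omission can only help the endpoint when revision is prompted by a poor threshold.

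The effect is unknown because no revision rate is given. At the planned 1.9 ± 1.2 V with 49 evaluable subjects, the conclusion turns at 10 revisions with a failing value of 3.5 V (20%), 5 at 5 V (10%) or 2 at 7.5 V (4%). With 36 evaluable, the counts are 6, 3 and 2. Below these counts the pass stands. The margin would differ if the unrevised mean were not 1.9 V. The figures also assume that every revision followed a threshold failure, which overstates the effect if some were done for other reasons.

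This is a matter to settle before the analysis. It is not an error in the sample size or in the choice of test.

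**What to change.** Keep the planned test as a 3-month, system-in-use endpoint.

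1. In Section 12.1.2.2, add a pre-specified sensitivity analysis covering every subject with an LV lead reposition, replacement or abandonment before the 3-month measurement, including those with no in-window value. Run it (a) with the last threshold recorded before the procedure and (b) with a failure value fixed in advance, for example across 3.5 V (Table 25-2) to 7.5 V (Section 5.1.1). Version (b) covers subjects whose last recorded value predates the failure or who have no numeric value.
2. Report the number of such subjects and the reasons for revision beside the primary result. Section 11.5 already requires the reason to be recorded.
3. As a minor clarification, state in Section 11.5 that the endpoint window stays on the first implant date after any revision, in line with the synopsis schedule and Section 11.1.

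Section 12.5.4 provides the route: an amended SAP approved before the primary analyses. The cost is a few sentences and one extra table. Sample size, visits and the primary test do not change. The downside is that the sensitivity result may look less favourable than the primary one.

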12.2. Secondary Safety and Effectiveness Objectives

To further characterize the safety, performance, and effectiveness of the Ingenio 2 CRT-P device, the following outcomes will also be summarized for all implanted and attempted subjects.

12.2.1.1. Secondary Safety Objectives

- Assessment of proper function of the PaceSafe-LVAT feature with special attention to:
 - inappropriate loss of capture due to LVAT (not related to lead dislodgement, connection issue, etc.) and
 - devices which show retry into LVAT followed by Latitude alert
- Assessment of reported events in relation to the use of MICS during all visits
- Assessment of all reported events in relation to the Quad Lead and Header

12.2.1.2. Secondary Effectiveness Objectives

- Collection of user experience with the PRM interface through the Product Experience Reporting at implant and during follow-up
- Assessment of LV pacing at implant and follow up (pacing threshold per vector, impedance per vector, % pacing)
- Assessment of battery voltage at the Latitude based Close-out visit, for all devices. A battery voltage \leq 75% of expected power level (based on the theoretical power consumption calculation in respect to the programmed parameters) will be investigated further.
- Assessment of POST: number of out of range impedance alerts not related to mitigating factor (header connection issue, lead failure, lead dislodgement, etc.)
- Assessment of the correlation between 6 minute walking test distance at 1 month and 3 months post-implant and for subjects with HRS < 50 and ≥ 50 .
- The HRS changes between 1 month follow-up and 3 month follow-up will be analyzed for all subjects, for subjects with HRS < 50 and ≥ 50 , and for subjects in a non-rate adaptive mode and with rate adaptive pacing.

All event data may be combined with data from Ingenio 2 devices enrolled into the Gentle study.

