Secondary Effectiveness Objectives	
 Collection of user experience with the programmer (PRM) interface through the Product Experience Reporting at implant and during follow-up Assessment of LV pacing at implant and follow up (pacing threshold per vector, impedance per vector, % pacing) Assessment of battery voltage at Latitude based Close-out Assessment of Post-Operative System Test (POST): number of out of range impedance alerts not related to mitigating factor (header connection issue, lead failure, lead dislodgement, etc.) Assess the correlation between 6 minute walking test distance at 1 month and 3 months post-implant and for subjects with heart rate score (HRS) < 50 and \geq 50 The HRS changes between 1 month follow-up and 3 month follow-up will be analyzed for all subjects, for subjects with HRS < 50 and \geq 50, and for subjects in a non-rate adaptive mode and with rate adaptive pacing: 
All event data may be combined with data from Ingenio 2 devices enrolled into the Gentle study.

Methodologies	
Method of Assigning Subjects to Treatment	The devices are fully commercially available and all subjects are planned to receive a CRT-P implant as part of their standard of care (SOC). The assignment of the specific Ingenio 2 device is physician's choice and will consider leads currently in place from previous devices and planned new leads (e.g., Acuity X4 and/or other LV leads).

Rally-CRT-P	

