12.4.2. Descriptive Statistical Methods

Descriptive statistical methods will be used to summarize the data from this study, with hypothesis testing performed for the primary endpoints. Unless otherwise stated, all statistical testing will be one-sided and will be performed using a significance (alpha) level of 0.05.

Continuous variables as a minimum will be described by number of non-missing observations (n), arithmetic mean (Mean), SD, minimum (Minimum), median (Median), and maximum (Maximum). One additional decimal point for mean and median and 2 additional decimal points for SD will be used.

Categorical variables will be presented using the number of non-missing observations (n) or the number of subjects in the population (N) as applicable and percentages (%). Percentages will be rounded to one decimal place. Unless otherwise stated, two-sided 90% CIs will be provided when relevant. The two-sided 90% CI will be presented as it provides:

- the one-sided 95% lower limit when the upper bound is ignored to assess superiority.
- the one-sided 95% upper limit when the lower bound is ignored to assess superiority.

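### The only analysis named for six-minute walk distance is a month-1 to month-3 correlation, which shows neither the direction nor the size of a mean change; a paired change with its 90% CI should be added

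*Combined protocol and SAP*

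**What the plan says.** - **Walk distance.** Section 12.2.1.2 names one analysis: "Assessment of the correlation between 6 minute walking test distance at 1 month and 3 months post-implant", also for subjects with HRS below 50 and at or above 50. Section 7.4 has the same wording, and the Synopsis has "Assess the correlation between 6 minute walking test distance at 1 month and 3 months post-implant".
- **HRS.** The next bullet does name a change: "The HRS changes between 1 month follow-up and 3 month follow-up will be analyzed for all subjects". It is split at HRS 50 and "for subjects in a non-rate adaptive mode and with rate adaptive pacing". The visit whose HRS sets the cut is not given.
- **General handling.** Section 12.2 says that "the following outcomes will also be summarized for all implanted and attempted subjects". Section 12.4.2 adds "Continuous variables as a minimum will be described by number of non-missing observations (n), arithmetic mean (Mean"), SD, minimum, median and maximum, and "two-sided 90% CIs will be provided when relevant".
- **Walk conditions.** In section 11.7 the month-1 walk is brisk and in a non-rate-adaptive mode. In section 11.8 the month-3 walk is vigorous and in the mode set at month 1. The six-minute walk appendix has subjects walk at their own pace.
- **Exceptions to the pacing mode.** Sections 10.4 and 11.6 allow rate-adaptive pacing before month 1 for a known need. Section 18.3 allows early sensor optimisation for other subjects.

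**The concern.** Walk distance is listed under effectiveness, and the Introduction says the study should improve understanding of the clinical impact of optimised rate-adaptive pacing. The two walks fall on either side of the month-1 programming step, so the within-subject change is the quantity closest to that aim. A correlation measures whether subjects keep their rank and spacing. It does not measure whether they walk further.

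Visit means show a direction, but they are computed on the observations available at each visit. They can therefore move through loss of subjects alone, and the plan specifies no interval for the change.

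Two smaller gaps concern HRS. The visit that sets the cut at 50 decides the sign of a regression-to-the-mean artefact in the strata. The mode split does not separate subjects who switched at month 1 from those already rate adaptive, who do not switch between the two HRS measurements.

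**Working it through.** **1. The plan's own figure.** The documents give no figure for walk distance. What fixes precision is the sample size in section 12.3: 49 evaluable, and the minimum to "account for up to 20% attrition is 62".
- 49/(1 − 0.20) = 61.25, rounded up to 62. The planned loss is 62 − 49 = 13.
- Exact binomial test, 87.5% against 97.5%, one-sided 0.05: n = 49 succeeds with at least 47 complication-free (alpha 0.0461, power 87.6%); n = 48 has power 66.2%. The 49 and the 62 both reproduce.

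Every mean, SD and correlation below is assumed.

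**2. Uniform shift.** For any constant c, corr(X, Y + c) = corr(X, Y). Take 49 pairs with mean 350 m, SD 100 m and r = 0.80 exactly, and shift every month-3 distance:
- −50 m: r = 0.80; paired change −50 m (90% CI −65 to −35)
- 0 m: r = 0.80; paired change 0 m (−15 to +15)
- +50 m: r = 0.80; paired change +50 m (+35 to +65)

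**3. Precision of the paired change.** Half-width = t(0.95, n − 1) × SD × √(2(1 − r))/√n. At n = 49 the multiplier of the SD of change is 0.240.
- SD 80 m, r = 0.9: SD of change 35.8 m, half-width 8.6 m
- SD 100 m, r = 0.8: 63.2 m, half-width 15.2 m
- SD 120 m, r = 0.7: 120 × √0.6 = 93.0 m, half-width 22.3 m

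In a stratum of 20 (size assumed) the range is 13.8 to 35.9 m.

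**4. Drift of visit means with no within-subject change.** Artefact = share lost between the walks × the amount by which the lost subjects walked less at month 1 (assumed 50 to 100 m).
- 4 of 53 lost, so that 49 remain: 4/53 × 50 = 3.8 m; 4/53 × 100 = 7.5 m
- Extreme, all 13 of 62 lost between the walks: 13/62 × 50 = 10.5 m; 13/62 × 100 = 21.0 m

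The paired change among subjects with both walks stays at 0.

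**5. HRS cut at 50 with no true change.** With a month-1 cut and z = (50 − mean)/SD, the ≥50 stratum changes by −(1 − ρ) × SD × φ(z)/(1 − Φ(z)), and the <50 stratum by +(1 − ρ) × SD × φ(z)/Φ(z). At SD 20 and ρ = 0.8, for ≥50 and <50 respectively:
- mean 35: −5.3 and +1.6 points
- mean 50: −3.2 and +3.2
- mean 65: −1.6 and +5.3

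A month-3 cut reverses every sign. The all-subject change has no cut and so no artefact of this kind.

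**6. Would covariate adjustment rescue the strata?** Regress month-3 HRS on month-1 HRS plus the stratum indicator, at SD 20 and ρ = 0.8. With no true change, the adjusted contrast is within about 0.1 of zero. With a real reduction of 20% of month-1 HRS, the true between-stratum difference is −6.4 to −6.9 points, yet the adjusted contrast is again within 0.1 of zero. In both cases expected month-3 HRS is linear in month-1 HRS, so the covariate absorbs everything and the indicator measures only a jump at 50.

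**The case against.** The best defence is section 12.4.2. Its list is a minimum and it allows 90% CIs where relevant, so a paired change is not ruled out and a shift in visit means would be seen. That stands as far as it goes: the gap is that no within-subject change is specified, not that change would be invisible. It is also fair that r can respond when subjects change by different amounts. Invariance is exact only for a uniform shift or a positive linear rescaling, though r gives no mean change in any case. The bullet's phrase about HRS groups is unclear and might relate distance to HRS group, but no reading names a change in distance.

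The differing walk instructions are a real limit. A paired change would carry any effect of the instruction into a precise-looking estimate.

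Three stronger readings are tempting and are not supported:
- **A false gain of 10 to 21 m from drop-out.** This needs the whole attrition allowance to fall between two visits about two months apart. The 20% in section 12.3 is a total.
- **Adjusting the HRS strata for month-1 HRS.** A near-zero adjusted contrast looks like a cure, but step 6 shows that the adjustment removes real baseline-dependent change as well.
- **At most 10 subjects already rate adaptive.** The limit of 10 in section 10.4 covers only a known indication and may be exceeded with sponsor approval. The early optimisation in section 18.3 has no limit.

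**Conclusion.** The point holds as a small, cheap improvement. The one analysis named for walk distance cannot show the direction or size of a mean change, although the neighbouring HRS objective names a change over the same interval. A paired change would be estimated to within about 9 to 22 m at n = 49, given SD 80 to 120 m and r 0.7 to 0.9. The bias it avoids in visit means is about 4 to 8 m in a moderate case and 10 to 21 m only in the extreme one. The invariance of r needs no assumption; the sizes rest wholly on assumed values.

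A reader might infer that the paired change would measure the effect of rate-adaptive programming. It would not: the study has one group, not every subject is reprogrammed at month 1, and the result describes only subjects with both walks. Nor does the point touch the sample size, a primary endpoint or a success criterion.

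**What to change.** In section 12.2.1.2, and to match in section 7.4 and the Synopsis:
- Add the paired change in walk distance (month 3 minus month 1) among subjects with both walks, with the two-sided 90% CI of section 12.4.2, overall and by HRS below 50 and at or above 50, using month-1 HRS for the strata.
- Keep the correlation as supplementary, and report how many subjects lack one or both walks.
- State that the result is descriptive and uncontrolled. Reconcile the walk instructions in sections 11.7, 11.8 and the walk appendix, or name the difference as a limit on interpretation.
- For the HRS change, state that the cut at 50 uses the month-1 value, that regression to the mean affects the stratum changes, and that the all-subject change is the main result. Do not add a covariate-adjusted stratum contrast.
- In the mode split, show subjects already rate adaptive before month 1 separately from those switched at month 1, without presuming the size of the first group.

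The cost is a few lines of text and slightly more descriptive output. Walk distance and HRS are already collected at both visits, and section 12.5.4 provides for an amended SAP before the primary analyses. Some groups may be too small for a useful interval.
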